6.1.2 Serious Adverse Event (SAE)

A serious adverse event is an undesirable sign, symptom or medical condition which:

- Results in death
- Is life threatening (defined as an event in which the subject was at risk of death at the time of the event; it does not refer to an event which hypothetically might have caused death if it were more severe)
- Requires inpatient hospitalization or causes prolongation of existing hospitalization (see note below for exceptions) > 24 hours

A Phase I/II trial of combination immunotherapy with nivolumab and a CCR2/CCR5 dual antagonist (BMS-813160) with or without GVAX following chemotherapy and radiotherapy for locally advanced pancreatic ductal adenocarcinomas (PDACs)

- Results in persistent or significant disability/incapacity
- Is a congenital anomaly/birth defect (note: reports of congenital anomalies/birth defects must also be reported on the Pregnancy Supplemental Form)
- Is an important medical event (defined as a medical event(s) that may not be immediately life-threatening or result in death or hospitalization but, based upon appropriate medical and scientific judgment, may jeopardize the subject or may require intervention [e.g., medical, surgical] to prevent one of the other serious outcomes listed in the definition above.). Examples of such events include, but are not limited to, intensive treatment in an emergency room or at home for allergic bronchospasm; blood dyscrasias or convulsions that do not result in hospitalization.)
- Is a new cancer (that is not a condition of the study)
- Is associated with an overdose
- Is a pregnancy
- Is a potential drug-induced liver injury (DILI)
- Is a suspected transmission of an infectious agent (e.g. pathogenic or nonpathogenic) via the study drug.

Events **not** considered to be serious adverse events are hospitalizations for the following:

- A visit to the emergency room or other hospital department < 24 hours, that does not result in admission (unless considered an important medical or life-threatening event)
- Elective surgery, planned prior to signing consent
- Admissions as per protocol for a planned medical/surgical procedure or to facilitate a procedure
- Routine health assessment requiring admission for baseline/trending of health status (e.g. routine colonoscopy)
- Medical/surgical admission for purpose other than remedying ill health state and was planned prior to entry into the study. Appropriate documentation is required in these cases
- Admission encountered for another life circumstance that carries no bearing on health status and requires no medical/surgical intervention (e.g. lack of housing, economic inadequacy, care-giver respite, family circumstances, administrative).

Although pregnancy, overdose, potential drug-induced liver injury (DILI), and cancer are not always serious by regulatory definition, these events must be handled as SAEs (see **Section 6.5** for details).

Any component of a study endpoint that is considered related to study therapy should be reported as an SAE (e.g. death is an endpoint, if death occurred due to anaphylaxis, anaphylaxis must be reported).

A Phase I/II trial of combination immunotherapy with nivolumab and a CCR2/CCR5 dual antagonist (BMS-813160) with or without GVAX following chemotherapy and radiotherapy for locally advanced pancreatic ductal adenocarcinomas (PDACs)

An SAE report should be completed for any event where doubt exists regarding its seriousness.

All SAEs will be reported to the IND Sponsor and BMS Worldwide Safety, whether related or not related to study drug.

If the investigator believes that an SAE is not related to study drug, but is potentially related to the conditions of the study (such as withdrawal of previous therapy or a complication of a study procedure), the relationship should be specified in the narrative section of the SAE Report Form.

6.1.3 Non-Serious Adverse Event

A non-serious adverse event is an AE not classified as serious.

Any significant worsening noted during interim or final physical examinations, electrocardiograms, X-rays, and any other potential safety assessments, whether or not these procedures are required by the protocol, should also be recorded as a non-serious or serious AE, as appropriate, and reported accordingly.

Non-serious Adverse Events are to be provided to BMS in aggregate via interim or final study reports as specified in the agreement or, if a regulatory requirement [e.g. IND US trial] as part of an annual reporting requirement.

6.2 Relationship and Grading

The relationship of an AE to the administration of the study drug is to be assessed by the investigator according to the following definitions:

- No (unrelated, not related, no relation): The time course between the administration of study drug and the occurrence or worsening of the adverse event rules out a causal relationship and another cause (concomitant drugs, therapies, complications, etc.) is suspected.
- Yes (related): The time course between the administration of study drug and the occurrence or worsening of the adverse event is consistent with a causal relationship and no other cause (concomitant drugs, therapies, complications, etc.) can be identified.

The following factors should also be considered:

- The temporal sequence from study drug administration - The event should occur after the study drug is given. The length of time from study drug exposure to event should be evaluated in the clinical context of the event.

- Underlying, concomitant, intercurrent diseases - Each report should be evaluated in the context of the natural history and course of the disease being treated and any other disease the subject may have.
- Concomitant medication - The other medications the subject is taking or the treatment the subject receives should be examined to determine whether any of them might be recognized to cause the event in question.
- Known response pattern for this class of study drug - Clinical and/or preclinical data may indicate whether a particular response is likely to be a class effect.
- Exposure to physical and/or mental stresses - The exposure to stress might induce adverse changes in the recipient and provide a logical and better explanation for the event.
- The pharmacology and pharmacokinetics of the study drug - The known pharmacologic properties (absorption, distribution, metabolism, and excretion) of the study drug should be considered.

Assessment of Grade:

The investigator will make an assessment of grade for each AE and SAE reported during the study, which will be recorded in the CRF. The assessment will be based on the National Cancer Institute's CTCAE (Version 5.0) and graded as shown below:

- Grade 1: Mild; asymptomatic or mild symptoms; clinical or diagnostic observations only; intervention not indicated
- Grade 2: Moderate; minimal, local or noninvasive intervention indicated; limiting age-appropriate instrumental activities of daily living
- Grade 3: Severe or medically significant but not immediately life-threatening; hospitalization or prolongation of hospitalization indicated; disabling; limiting self-care activities of daily living
- Grade 4: Life-threatening consequences; urgent intervention indicated
- Grade 5: Death related to AE

Any AE that changes in grade during its course will be recorded in the CRF at the highest level experience by the subject.

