1.4 Primary Endpoints

1.4.1 Primary Endpoint in phase I portion of study: Safety

- Study-related adverse events according to National Cancer Institute Common Toxicity Criteria for Adverse Events (NCI CTCAE; Version 5.0) that occur on or after Cycle 1, Day 1 immunotherapy.
- Incidence, nature and severity of all adverse events that occur on or after Cycle 1, Day 1.

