The Phase II portion is a randomized two-arm study to evaluate immune response, efficacy and safety of the combination of nivolumab and CCR2/CCR5 dual-antagonist (BMS-813160) with and without GVAX. We will be monitoring the toxicities for each arm in the Phase II portion, and if we observe >33% unacceptable toxicities in the first 6 patients or any time afterwards in any arm, we will halt the enrollment pending safety evaluations.

DLTs will be assessed in the first cycle of Phase I, starting Cycle 1 Day 1 through prior to initiation of Cycle 2. Unacceptable toxicities will be used to monitor safety from Cycle 2 Day 1 of Phase I through to end of study treatment and from Cycle 1 Day 1 of Phase II through to end of treatment. During periods of standard of care treatment (FOLFIRINOX-based chemotherapy, SBRT, Surgery) only AEs considered related to study treatment will be collected. If patients develop adverse events (AEs) to any of the three immunotherapies

A Phase I/II trial of combination immunotherapy with nivolumab and a CCR2/CCR5 dual antagonist (BMS-813160) with or without GVAX following chemotherapy and radiotherapy for locally advanced pancreatic ductal adenocarcinomas (PDACs)

(BMS-813160, nivolumab or GVAX) leading to its/their discontinuation, they will be taken off the trial.

All patients will undergo standard of care evaluations consisting of history and physical, CT of the chest/abdomen/pelvis or MRI abd/pelvis and non-contrast CT chest (if do not tolerate contrast) to evaluate for local progression and metastatic disease while they are on study.

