6. ADVERSE EVENTS: LIST AND REPORTING REQUIREMENTS

This study will use the descriptions and grading scales found in the revised National Cancer Institute Common Terminology Criteria for Adverse Events (CTCAE) Version 5.0 for adverse event reporting that can be found at http://ctep.cancer.gov/protocolDevelopment/electronic_applications/ctc.htm.

Information about all adverse events, whether volunteered by the patient, discovered by investigator questioning, or detected through physical examination, laboratory test or other means, will be collected, recorded, and followed as appropriate.

The Principal Investigator has the primary responsibility for continuous internal monitoring for safety, protocol compliance, and identification, grading, coding, and required reporting of all anticipated and unanticipated adverse events and protocol problems. Although this responsibility is usually shared among the Principal Investigator, research nurse, and data manager, the Principal Investigator is ultimately responsible for grading and attribution of all events.

All adverse events experienced by patients will be collected and reported from the first dose of the investigational agent, throughout the study, and will only be followed for 4 weeks unless related to the investigational agent. Only toxicities considered related to study procedures or treatment will be collected from the time of surgery until the start of Cycle 2.

A Phase I/II trial of combination immunotherapy with nivolumab and a CCR2/CCR5 dual antagonist (BMS-813160) with or without GVAX following chemotherapy and radiotherapy for locally advanced pancreatic ductal adenocarcinomas (PDACs)

All Serious Adverse Events (SAEs) will be collected from the first day of immunotherapy treatment through 100 days after the end of treatment or until a new antineoplastic treatment is initiated, whichever occurs first. All SAEs whether related or not related to study drug must be reported to the IND Sponsor and BMS Worldwide Safety. If applicable, SAEs must be collected that relate to any later protocol-specified procedure (e.g. a follow-up skin biopsy).

Subjects who have an ongoing adverse event related to the study procedures and/or medication(s) may continue to be periodically contacted by a member of the study staff until the event is resolved or determined to be irreversible by the investigator.

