6.4 Handling of Expedited Safety Reports

In accordance with local regulations, the IND Sponsor will notify investigators of all SAEs that are unexpected (i.e. not previously described in the Investigator Brochure), and definitely, probably, or possibly related to nivolumab, BMS-813160 or GVAX. This notification will be in the form of an expedited safety report (ESR) that is to be faxed to the investigators and the study coordinators within 48 hours. Upon receiving such notices, the investigator must review and retain the notice with the Investigator's Brochure and where required by local regulations, the investigator will submit the ESR to the appropriate IRB. The investigator and IRB will determine if the informed consent requires revision. The investigator should also comply with the IRB procedures for reporting any other safety information.

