6.5 Reporting

6.5.1 General

All adverse events (both expected and unexpected) will be captured on the appropriate study-specific Case Report Forms (CRFs), with the exception of unrelated adverse events that occur during the standard of care treatment periods. The standard of care treatment periods include FOLFIRINOX-based chemotherapy administration and SBRT treatment through initiation of Cycle 1 of combination immunotherapy and from surgical resection or Nanoknife procedure through initiation of Cycle 2 combination immunotherapy. All AEs collected will be reported in aggregate in the final study report, which must be provided to BMS. No individual or expedited reporting is required.

All serious adverse events, regardless of causality to study drug, including those thought to be associated with protocol-specified procedures will be reported promptly to the IND Sponsor and BMS Worldwide Safety within 24 hours of recognition, with the exception of unrelated SAEs that occur during the standard of care treatment periods as defined above. Serious adverse events should be reported using the form found in **Appendix B**. If this falls on a weekend or holiday, an email notification is acceptable but must be followed by an SAE reporting form on the next business day.

SAE reports and any other relevant safety information are to be sent to:

IND Sponsor ([name]): [REDACTED]

BMS: [REDACTED]

After the initial AE or SAE report, the investigator is required to proactively follow each subject and provide further information to the safety department in regard to the subject's condition.

All AE(s) and SAE(s) will be followed until:

- Resolution

A Phase I/II trial of combination immunotherapy with nivolumab and a CCR2/CCR5 dual antagonist (BMS-813160) with or without GVAX following chemotherapy and radiotherapy for locally advanced pancreatic ductal adenocarcinomas (PDACs)

- The condition stabilizes
- The event is otherwise explained
- The subject is lost to follow-up
- Death

As soon as relevant information is available, a follow-up SAE report will be submitted to the IND Sponsor and BMS.

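### Section 6.2 leaves ambiguous adverse events unclassified, and the collection and SAE rules from surgery to Cycle 2 conflict with the all-AE safety endpoint and with each other

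*Combined protocol and SAP*

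**What the plan says.** **Attribution.** Section 6.2 has two categories. An event is related if the time course is "consistent with a causal relationship and no other cause (concomitant drugs, therapies, complications, etc.) can be identified". It is unrelated if the time course "rules out a causal relationship and another cause (concomitant drugs, therapies, complications, etc.) is suspected". The SAE form in Appendix B offers the same two choices for each drug. Section 6.4, however, acts on unexpected SAEs that are "definitely, probably, or possibly related to nivolumab, BMS-813160 or GVAX", and Section 6.5.3.1 uses possibly related as the trigger for FDA reports.

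**Collection.** Section 6 states: "Only toxicities considered related to study procedures or treatment will be collected from the time of surgery until the start of Cycle 2". Sections 1.7 and 4.1 repeat this rule. A later paragraph of Section 1.7 is narrower and omits study procedures: in standard-of-care periods "only AEs considered related to study treatment will be collected". Section 6.5.1 words it the other way round: everything goes on the case report form except unrelated events in those periods, one of which runs from resection or NanoKnife to Cycle 2.

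**Endpoint.** Section 1.4.1 lists "Incidence, nature and severity of all adverse events that occur on or after Cycle 1, Day 1". Sections 1.5.1 and 12.1 agree, and none makes a peri-operative exception.

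**SAEs.** Section 6.1.2 says: "All SAEs will be reported to the IND Sponsor and BMS Worldwide Safety, whether related or not related to study drug". The introduction to Section 6 says the same. Section 6.5.1 requires 24-hour reporting "with the exception of unrelated SAEs that occur during the standard of care treatment periods as defined above".

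**Monitoring.** In Section 4.7 the grade 3 and grade 4 or higher unacceptable toxicities must be treatment-related. In Phase II they count from Cycle 1 Day 1 to end of treatment, which spans surgery. Section 4.6 limits DLTs to events without an alternate cause, over a window that runs up to Cycle 2.

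**The concern.** After a pancreatic resection nearly every complication has another candidate cause, so the strict test for *related* is hard to meet at the point where it decides whether an event is recorded. Drug effects remain plausible then. BMS-813160 continues to the day before surgery. Cycle 1 starts within two weeks of SBRT and surgery falls five to seven weeks after SBRT, so the operation comes about 3 (5 − 2) to 7 (7 − 0) weeks after the nivolumab dose.

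Elsewhere in the treatment period all events are collected, so a doubtful attribution can be revisited. Between surgery and Cycle 2 an event judged not related may leave no study record. At stake are the completeness of the safety endpoint (primary in Phase I, secondary in Phase II), consistent SAE reporting, and the count behind the Phase II stopping rule.

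**Working it through.** **Step 1: follow each kind of event through the rules, from surgery to Cycle 2.**

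| Event | Category in 6.2 | Collected under Section 6, 1.7, 4.1? | Exempt under 6.5.1? | If serious |
|---|---|---|---|---|
| Timing excludes drug, other cause suspected | Unrelated | No, unless tied to a study procedure | Yes | Required by 6 and 6.1.2, exempted by 6.5.1 |
| Timing fits, another cause possible | None | No, unless tied to a study procedure | No, because it is not unrelated | Required by 6, 6.1.2 and 6.5.1; possibly related for 6.4 and 6.5.3.1, but the form cannot record that |
| Timing fits, no other cause | Related | Yes | No | Required throughout |

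The first row shows that the all-AE endpoint is incomplete in this window on any reading, and that the SAE rules contradict each other. In the second row, loss of a non-serious event depends on which collection sentence the site follows.

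**Step 2: extent.** Section 1.7 expects 30-40% to be resected, which is 0.30 × 5 = 1.5 to 0.40 × 5 = 2 patients in a five-patient arm, plus any NanoKnife patients. The window is 6 to 12 weeks (42 to 84 days) for each.

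**Step 3: reproduce the stopping-rule table in Section 12.5.** The rule stops at 2 or more events in up to 6 patients, or 3 or more in 7 to 9. With at most 9 patients,

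P(stop) = 1 − [P(X₆=0)·P(Y₃≤2) + P(X₆=1)·P(Y₃≤1)],

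where X₆ and Y₃ are binomial counts in the first 6 and the next 3 patients. At a risk of 0.33: 1 − [0.0905 × 0.9641 + 0.2673 × 0.7452] = 0.714.

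| Risk | 0.10 | 0.20 | 0.25 | 0.30 | 0.33 | 0.40 | 0.45 |
|---|---|---|---|---|---|---|---|
| Plan (5000 simulations), % | 12.2 | 37.8 | 52.8 | 65.3 | 71.6 | 83.7 | 89.8 |
| Exact, % | 12.5 | 38.8 | 52.4 | 64.8 | 71.4 | 83.5 | 89.7 |

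The table reproduces within simulation error. Its risk is the risk of a *counted* event.

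**Step 4: illustrate under-counting.** The documents give no missed fraction, so one is assumed. Let s be the share operated on (0.30 to 0.40), with the same risk as other patients. Let f be the fraction of operated patients with a qualifying toxicity who have it only in this window and not called related. Then

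counted risk = p × (1 − s·f).

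At p = 0.33 and f = 0.5 this is 0.33 × 0.85 = 0.281 (s = 0.30) or 0.33 × 0.80 = 0.264 (s = 0.40). For five patients, P(X≥2) = 1 − (1−q)⁵ − 5q(1−q)⁴, with q the counted risk. This gives 0.532 at q = 0.33, 0.431 at 0.281 and 0.397 at 0.264.

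| f (assumed) | Counted risk at true 0.33 | Stop, 5 patients | Stop, up to 9 | Stop, up to 9, true risk 0.40 |
|---|---|---|---|---|
| 0 | 0.330 | 53.2% | 71.4% | 83.5% |
| 0.25 | 0.297-0.305 | 46.6-48.3% | 64.1-66.0% | 77.1-78.8% |
| 0.5 | 0.264-0.281 | 39.7-43.1% | 56.1-60.2% | 69.3-73.4% |
| 1 | 0.198-0.231 | 25.9-32.7% | 38.2-47.3% | 49.8-60.1% |

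Five is the planned size of Arms A and B (Section 12.2). Nine is the maximum that the Section 12.5 table implies.

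**The case against.** Limiting collection during standard-of-care periods is a deliberate choice, stated in several places, and the plan keeps more than a first reading suggests. Section 4.2.2.2 requires suspected immune-related events to be documented, with no surgical exception. Section 6 also reports grade 3 and 4 laboratory results that have worsened from baseline. Events related to study procedures are collected under the Section 6 wording. In Section 4.7 the eye events and potential drug-induced liver injury do not carry the treatment-related wording, although the liver definition has its own test for other causes. Adverse events are evaluated again at Cycle 2 Day 1. Patients who are not surgical candidates have no gap. All of this stands.

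A reader might therefore go too far in three ways:

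- **That peri-operative toxicity drops out of the endpoint, the stopping rule and SAE reporting altogether.** The ambiguous event is not unrelated under 6.2, so 6.5.1 does not exempt it, and Sections 6 and 6.1.2 require every SAE. Toxicity that delays surgery occurs before the window opens.
- **That the safety endpoint cannot be computed.** One of its components is study-related events. The gap affects the all-AE component, in one window, for a minority.
- **That the stopping probability collapses.** Halving the risk in every patient (0.33 to 0.165) gives 1 − 0.835⁵ − 5 × 0.165 × 0.835⁴ = 19% in a five-patient arm. That is below the 26% reached if every operated patient's event were missed at 40% operated, so it does not describe this window.

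The rule's action is also to halt enrolment, which closed on December 19, 2022. Only the assignment of remaining patients to Arm C could still be affected.

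None of this removes the gap in 6.2, the contradiction on SAEs, or the mismatch between endpoint and collection.

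**Conclusion.** The point holds as three conflicts within the text: a two-way attribution scale that leaves out ambiguous events while other sections act on possibly related ones; an all-AE endpoint set against related-only collection from surgery to Cycle 2; and two incompatible rules for unrelated SAEs in that window. The all-AE endpoint is certainly incomplete there for operated patients. Loss of drug-caused events, including from the treatment-related items of Section 4.7, is possible but not certain.

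The fall in stopping probability at a true risk of 33% (53% to 40-43% with five patients, 71% to 56-60% with up to nine) rests on an assumed missed fraction of one half, equal risk in operated and other patients, and 30-40% operated. It indicates scale and is not an estimate. With enrolment closed, the lasting harm is mainly incomplete safety data. This should be corrected, but it does not invalidate the safety analysis.

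**What to change.** 1. In Section 6.2, make the two categories exhaustive, for example by defining related as a reasonable possibility that study drug contributed. Use the same terms in Sections 6.4 and 6.5.3.1 and on the Appendix B form.
2. From Cycle 1 Day 1, record all SAEs and all grade 3 or higher events regardless of attribution, including from surgery or NanoKnife to Cycle 2. Align Sections 1.7, 4.1, 6 and 6.5.1. If grade 1 and 2 events in that window stay limited to related ones, say so in the endpoint wording of Sections 1.4.1, 1.5.1 and 12.1.
3. Remove the conflict between Section 6.5.1 and Sections 6 and 6.1.2 on unrelated SAEs in this window.
4. Tabulate events from surgery to Cycle 2 separately in the analyses of Sections 12.3 and 12.5, and report the gap for patients who have already passed through it.
5. Reconcile the attribution wording of Sections 4.6 and 4.7 with Section 6.2. Because Section 4.9 ties those sections to treatment discontinuation, this review proposes no new DLT or stopping definition.

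The cost is protocol and form wording, plus modest data entry over 6 to 12 weeks for the minority who are operated on. Reported related-event rates will be higher under the broader definition, and the report should explain why.
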